Fortunately exercise and NMES can improve local blood flow, exercise capacity and muscle mass.⁷ Banerjee found an average improvement of 0.24L in peak VO₂ when using NMES to increase strength in healthy sedentary adults.⁸ Maillefert found an increase in exercise capacity and muscle volume when low frequency NMES was used in those with HF.⁹ While this was a small sample, peak VO₂ increased 2.4 ml/kg/min, 6-minute walk test (6MWT) saw an improvement of 40 meters. Maillefert found low frequency NMES was safe, well tolerated and effective.⁹ In the systematic review by Sillen, in the nine HF studies using NMES as an intervention, researchers reported NMES was safe, but the protocol's varied widely and some of the patients dropped out due to discomfort.¹⁰

The hypothesis is that by using NMES, patients with HF will, in part, reverse the muscle wasting that occurs with HF and actually increase muscle mass and strength.^{20,21} With this increase in muscle, it is expected that patients will become more active, thus reversing the downward spiral that has been observed with doing less leading to less ability. One of the key factors in choosing this modality is that patients only need to apply the electrodes to their thighs and then sit back and let the machine do the work. Patients will be instructed to also add active quadriceps muscle contraction during the passive NMES contraction to decrease any discomfort and also to aid the building of muscle.²² Thus, NMES is used as the first step in an exercise program that is tailored for this very difficult population in order to improve exercise initiation, adherence, and sustained practice. Bruckenthal suggests in order to improve attitudes and adherence towards exercise by those with HF we need to increase the entertainment value or likeability of the options.²³ Being able to begin an exercise program without getting short of breath or having to invest a lot of energy in a population that is highly fatigued and short of breath, should improve the likeability and practicality of the option. With the increase in strength the patient may begin to feel some success which may then lead to increases in other activities leading to an overall improvement in exercise tolerance, improved functional ability, quality of life, and participation formal exercise programs.

Innovation

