Specific Aim 3: Assess the effect of NMES on HF symptoms and health-related quality of life (HRQOL). We will use the Memorial Symptom Assessment Scale-HF and Minnesota Living with Heart Failure Questionnaire (MLHFQ) to evaluate this aim. We hypothesize that HRQOL will increase while HF symptoms decrease.

Specific Aim 4: Evaluate the effect of NMES on enrollment and utilization of a formalized exercise program. We hypothesize that patients in the NMES group will be more likely to participate in a formalized exercise plan following the intervention than the sham group.

We will use a double blinded, randomized controlled longitudinal study design to determine if NMES will increase muscle mass and strength, decrease sitting and lying time, and improve HF symptoms and exercise capacity thus improving likelihood of engagement with a structured exercise program. Patients will be randomized to either intervention that includes NMES or to a sham/wait list control group.

Importance of the Knowledge to be gained

Research has shown that patients with HF see significant improvement in their HF symptoms, decrease hospitalizations, and find improvement in their overall health when they follow a prescribed exercise regimen. Many patients are not willing or able to begin exercising or discontinue the exercise regimen once they do start one due to high levels of fatigue and shortness of breath due to muscle wasting that occurs with HF. Having a lower starting point (starting with passive NMES) for exercise and building muscles up before enrolling in a cardiac rehabilitation program to meet the current exercise recommendations will likely improve the success for patients in being able to exercise. It is expected that all patients will benefit from a formalized exercise program regardless of NMES or Sham randomized group.

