gentle pumping sensation is felt. Participants will direct the amount of stimulation acceptable on both thighs to improve acceptance of the modality.^{10,24,29-31} To assist better tolerance large electrodes (2x4) will be used and participants will also be instructed to be in a seated position with chair close to the wall so that their leg is 90-degree angle and then push against the wall to decrease any uncomfortable feeling during the contraction. For the Sham group, electrodes will follow the same landmarks, but the stimulation will only increase to an intermittent tingling sensation with the machine setting on TENS instead of NMES which is not enough to make noticeable changes in muscle mass or circulation.³² Participants in both groups will be given written instructions and contact information of the person (RA) to contact should there be any problems or concerns with the intervention. All participants will do a return demonstration to assure proper knowledge has been gained. Adherence to the study protocol will be determined by the amount of time the EMPI machine records that it was used, the intensities utilized along with verbal verification during the weekly phone calls.

NMES Protocol Summary

- 5 sessions per week for 6 weeks done independently at home, with 15 minutes per session (15 stimulations per day/session, 15 seconds stimulation on, 15 seconds recovery time) to both legs.
- Intervention group only: We expect the participant to develop tolerance to the treatment and thus increase the intensity of the NMES over time.
- At the end of the trial, the participants will return to have all measures repeated. Sham group will then be offered the active treatment. In previous HF studies (non-NMES) done by the mentor of this grant, no participants have accepted the offer of the intervention after completion of the sham/control so this number is expected to be very small.
- Participants will be encouraged to begin a formalized exercise plan such as Silver Sneakers, a home based cardiac rehabilitation or institutional cardiac rehabilitation program.
- Finally, 3 months after the intervention/sham was completed participants will return one final time to have all measures repeated to allow for evaluation of activity levels following completion of the intervention.

Retention

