7. Set “Cycle” to 15S, then press the bottom left button to progress to “Span”
8. Set “Span” to 50%, then press the bottom left button to progress to “Mode”
9. Set “Mode” at MOD, then Press OK
10. Now the machine is set up for participant to test the comfort level.

Once the Data collector has told you the participant is ready for the intervention explain the machine to them by giving them the EMPI handout and going through each step with the participant following the directions and you clarifying when necessary. Make sure a garbage can and table with a bowl for warm water and wash cloth and towel is within reach, (show them how to use the trimmer if necessary), give them the EMPI handout, go through each step of the process with them. Once the patches are placed and the participant is ready to turn on the machine, show them the picture on page 3 and explain the need to use the on/off button and the increase/decrease intensity buttons. Have them start increasing the intensity on either channel slowly at first and closely monitor their reactions to it. For this intervention we are just looking for a general “feeling it”. They should not increase the intensity to the point where a muscle contraction happens!

Once you are confident the participant settings are comfortable for the patient and only intensity needs to be adjusted, LOCK the device so the participant cannot change the settings themselves.

1. Press the Home button, config (right lower), locks (right lower)
2. Notice the NMES L. Muscles and press the right top button, which locks that option
3. Press the left lower button to bring up S. Muscles and press the right top button twice to get a circle with a line through it. Now that option will no longer show for participants. Repeat for TENS and Edema then press home and note only L. Muscles is an option besides config.

EMPI Standard Operating Procedure for setting up NMES

Machine Set up: do this before you see the participant. Please note, you may not need to make adjustments to the machine due to previous programming, so if the correct option is chosen move on to the next item.

1. Turn on machine
2. Press “Home” button
3. Press the NMES button (top left)
4. Large muscle (top left)
5. Press the Custom button (bottom right)
6. Change time to 15 minutes, then press bottom left button to progress to “off time”
7. Change Off time to 15 Seconds, then press bottom left button to progress to “rate”

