8. Increase “Rate” to 50Hz, then press the bottom left button to progress to “Width”
9. Leave “Width” at 300 to start. Press bottom left button to progress “waveform”.
10. Leave “waveform” at SYM/ASY
11. Change Cycling “LAG” for both legs at the same time.
12. Leave “Lag” at 0S
13. Leave “CH1 Ramp +” at 2S
14. Increase “ON TIME 1” to 11S
15. Leave “CH1 RAMP –” at 2S
16. Leave “CH2 Ramp +” at 2S
17. Increase “ON TIME 2” to 11S
18. Leave “CH1 RAMP –” at 2S, then press OK
19. Now the machine is set up for participant to test the comfort level.

Once the Data collector has told you the participant is ready for the intervention explain the machine to them by giving them the EMPI handout and going through each step with the participant following the directions and you clarifying when necessary. Make sure a garbage can and table with a bowl for warm water and wash cloth and towel is within reach, (show them how to use the trimmer if necessary), give them the EMPI handout, go through each step of the process with them. Once the patches are placed and the participant is ready to turn on the machine, show them the picture on page 3 and explain the need to use the on/off button and the increase/decrease intensity buttons. Have them start increasing the intensity on either channel slowly at first and closely monitor their reactions to it. The intensity needs to be strong enough to cause the muscle to contract. Demonstrate how actively using the muscle during the contraction lessens any discomfort.

20. If the participant reports the feeling is uncomfortable or “biting” adjust the “Rate” to make the sensation more “smooth”. Decrease the Rate by 5 to 45 then have the participant try again. (Can adjust in increments of ±1 to get the “best” feel for participants. Be sure to record the final setting you programmed into the machine in both Redcap and the participant call sheet.) To make adjustments to Rate, (you not the

participant!) press the home button, NMES, Custom, the press the left lower button until you see “Rate”, then use the right lower button to make the adjustment, then press OK and have the participant try again.

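### On the most likely reading, the trial compares NMES plus voluntary quadriceps contraction with sensory TENS alone, so a gain cannot be credited to passive stimulation

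*Combined protocol and SAP*

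**What the plan says.** The rationale presents a passive treatment. In the background text before the Innovation heading, patients apply the electrodes and then "sit back and let the machine do the work". Section 2, on the importance of the knowledge to be gained, argues from "Having a lower starting point (starting with passive NMES) for exercise". Aims 1-4 are worded as the effect of NMES.

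The same background text also says patients will be told to "add active quadriceps muscle contraction during the passive NMES contraction to decrease any discomfort and also to aid the building of muscle". Section 5 (Intervention and Sham/Wait List Control Conditions) gives a resisted form: seated near a wall with the leg at a right angle, participants "push against the wall to decrease any uncomfortable feeling during the contraction". For the sham group, Section 5 keeps the electrode landmarks, but "the stimulation will only increase to an intermittent tingling sensation with the machine setting on TENS instead of NMES".

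Section 12B has one set-up SOP per arm. The NMES version ends its teaching paragraph with "Demonstrate how actively using the muscle during the contraction lessens any discomfort". The TENS version has no corresponding sentence and says of participants: "They should not increase the intensity to the point where a muscle contraction happens". The participant handout for the Empi unit mentions neither the wall push nor active contraction.

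**The concern.** If only the NMES arm is taught to contract and push, the arms differ in two components: the level of stimulation, and voluntary work by the muscle group being trained. The protocol itself expects the second component to help build muscle. Thigh lean mass and thigh strength are the Aim 1 outcomes. The Biodex test in Section 5 is also done seated from 90 degrees of knee flexion, with the patient tightening the thigh and straightening the knee, so the wall push resembles the task on which strength is scored.

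What is at stake is attribution. The protocol hopes to offer NMES as a stepping stone to exercise, or as an option for people who cannot exercise, and says the data will support a larger grant application. A gain produced partly by voluntary effort but reported as an effect of passive stimulation would carry the wrong conclusion into that application.

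**Working it through.** **1. Who is taught the voluntary contraction?**
- Background text: refers to patients in general and names no arm. The sentence concerns contraction added to the NMES contraction.
- Section 5: refers to participants and names no arm. The sentence follows the description of raising NMES intensity and precedes the sham description.
- NMES SOP: active use of the muscle is demonstrated.
- TENS SOP: its teaching paragraph is nearly identical up to the intensity instruction, but has no demonstration. Intensity stays below the point of contraction, so a sham participant has no evoked contraction to push during.
- Handout: silent for both arms.

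NMES-only teaching is therefore an inference, but the one that best fits the texts together.

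**2. Can the design or analysis separate the components?** There are two arms. No arm receives NMES without voluntary contraction, and none receives TENS with it. The Section 8 model contains Group, Time and their interaction, so the Group terms carry both components together. Adherence is measured by device use time, intensities and verbal verification in the weekly calls. No count or measure of voluntary contraction is prescribed or named.

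**3. Upper bound on the voluntary work.** The NMES Protocol Summary gives 5 sessions a week for 6 weeks, so 5 x 6 = 30 sessions. It also gives 15 stimulations per session, 15 s on and 15 s off, in a 15-minute session. These do not agree: 15 x 30 s = 450 s = 7.5 min. The NMES SOP sets 15 min, 15 s off, and 2 + 11 + 2 = 15 s on (taking the ramps as additional to the on-time), so 900 s / 30 s = 30 stimulations.

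| Source | Per session | Over 30 sessions | On-time in total | On-time per session |
|---|---|---|---|---|
| Protocol Summary | 15 | 450 | 450 x 15 s = 112.5 min | 3.75 min |
| SOP timing | 30 | 900 | 900 x 15 s = 225 min | 7.5 min |

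These are counts of stimulations. They equal voluntary contractions only if every participant pushes through every stimulation for its full length, which no passage requires.

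**4. The plan's power figures, for context.** The calculation used a noncentral F, 2 groups by 3 times, N = 54, alpha 0.05, sphericity, and an assumed within-person correlation of 0.32 (the plan gives no number). For the group main effect, lambda = f² x 54 x 3 / (1 + 2 x 0.32), df 1 and 52. For the interaction, lambda = f² x 54 x 3 / (1 - 0.32), df 2 and 104. Power is 97.4% (f = 0.4, main), 68.4% (f = 0.25, main) and 93.6% (f = 0.25, interaction), within 2 points of the stated 97%, 69% and 95%. The point does not depend on these figures.

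**5. Illustration only.** Suppose components add and a share s of a medium effect comes from voluntary contraction. The part due to stimulation is then f = 0.25 x (1 - s). For s = 25%, 50% and 75%, f is about 0.19, 0.125 and 0.06, and interaction power for that part is about 73%, 38% and 12%. The shares are assumptions; nothing in the documents fixes them.

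**The case against.** The strongest reply is that the protocol tests a disclosed package. The background text states openly that active contraction is added and why, the aims say NMES and not passive NMES, and comparing a package with a near-inert sham is legitimate in a study that calls itself exploratory. This stands: the randomized comparison is valid for the package, and part of the defect is descriptive wording. It does not restore attribution to stimulation, which the passive framing invites.

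Several stronger readings are tempting, and the documents do not support them:
- *That NMES-only teaching is an established fact.* Neither the background nor Section 5 names an arm, although the Protocol Summary marks another item as applying to the intervention group only.
- *That the TENS SOP forbids voluntary effort.* It limits stimulation intensity so that no contraction is evoked; it does not address voluntary contraction.
- *That the NMES arm performs 450 or 900 resisted contractions.* Section 5 and the NMES SOP present the effort as a way to lessen discomfort, with no force or frequency set.
- *That the sessions move one arm past the protocol's own 10-minute threshold for regular exercise.* On-time is at most 7.5 minutes per session, and TENS sessions also last 15 minutes.
- *That the control receives nothing.* It receives sensory TENS.
- *That voluntary effort could not be recorded.* The weekly calls ask whether participants follow the protocol as taught, so a channel exists, though it does not name voluntary contraction.

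**Conclusion.** The point holds as a limit on attribution. On the most likely reading, the trial compares motor-level NMES plus voluntary quadriceps contraction with sensory TENS without it. A between-arm gain in thigh lean mass, strength or function would be evidence for that package and could not be assigned to passive stimulation. A reader might infer that the trial is invalid or can answer nothing; that goes too far.

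The size of the voluntary contribution is unknown, and two arms cannot estimate it. The conclusion rests on reading the difference between the two SOPs as intended. If the sponsor meant both arms to receive the instruction, the SOPs do not say so and the documents still need reconciling.

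**What to change.** Reconcile the background text, Section 5, both set-up SOPs and the participant handout so that the voluntary-contraction and wall-push instruction is stated by arm. Reconcile the stimulation count per session with the session length and the SOP timing as well.

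If the instruction stays NMES-only, restate the purpose, Aims 1-4 and the planned conclusion as NMES combined with voluntary quadriceps contraction versus sensory TENS without it. Drop passive as the description of the tested intervention, and do not attribute effects to stimulation alone. This costs wording only, with no extra patients or visits. The downside is a narrower conclusion.

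Giving the same instruction to both arms is an option for the sponsor to weigh, not a required change. It would isolate the level of stimulation, but it makes the sham less inert and may shrink the contrast, when stated power for a medium main effect is already only 69%.

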Section 4: Enrollment and Randomization

Patients who meet eligibility criteria will be referred to the investigator or the research assistant by cardiology, heart failure, or emergency room providers during their routine evaluation of patients eligible for participation in other heart failure research studies through the medical record system. In addition, a clinical research systems

request has been made to allow for notification to the PI the identification all heart failure patients admitted to the hospital so the PI or RA can screen for eligibility. In addition, [name] will release names and contact information for previous participants in her HF study to the PI if the participant has previously indicated they would like to be contacted for future research studies for screening to determine eligibility to participate in this study. The patient will then be contacted by a BISTRO team member for a full explanation of the study and determine interest in participating. If they are interested and are also willing to participate in the FIT Core study (IRB #170755085), an appointment for follow up discussion and possible consenting for both studies) will then be set up for the following week or two. At which time they will come to the school of nursing for final consideration, potential consenting, begin data collection.

In order to ensure that the two groups are comparable between treatment and sham interventions, the participants will be randomized according to gender. Randomization via minimization will be used in order to avoid an unbalanced number of women in the two comparison groups due to chance.²⁶ A file of the computer-generated random assignments will be kept by the research assistant so the PI/data collector remains blinded in a protected Box Health account.

Section 5: Study Procedures

Intervention and Sham/Wait List Control Conditions

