7. Demographic, and comorbidity status will be collected using a standard questionnaire, the Charlson comorbidity index and chart review. Demographics collected via patient report, will be used to characterize the participant sample and obtain potential confounding variables such as age, sex, race/ethnicity, marital status, education completed, employment status, NYHA classification, and income. The clinic record will also be used to evaluate additional hospital stays (**specific aim 4**), and medications. The Charlson Comorbidity Index is a method of evaluating the effects of comorbidities in patients based on the International Classification of Diseases diagnosis codes found in billing data. The comorbidity has an associated weight, based on the adjusted risk of mortality or resource use, and the sum of all the weights results in a single comorbidity score for a patient. The higher the score, the more likely the predicted outcome will result in mortality or higher resource use.⁵⁰

8. The PROMIS Fatigue Scale assess a range of self-reported symptoms, from mild feelings of tiredness to an overwhelming, debilitating, and sustained sense of exhaustion. Fatigue is measured by frequency, duration, and intensity as well as the impact of fatigue on physical, mental, and social activities.⁵¹ The fatigue short form-8 is universal rather than disease-specific and assess fatigue over the past seven days. Each question usually has five response options ranging in value from one to five. With 1= not at all, to 5=very much). To find the total raw score for a short form with all questions answered, sum the values of the response to each question. For example, the lowest possible raw score is 8; the highest possible raw score is 40. A higher PROMIS T-score represents more of the concept being measured. For negatively-worded concepts like fatigue, a T-score of 60 is one SD worse than average. By comparison, a fatigue T-score of 40 is one SD better than average Patient-Reported Outcomes Measurement Information System (PROMIS) 7-day recall Fatigue Item Bank (www.assessmentcenter.net/). Validity was determined by multidisciplinary panel made of nurses, physicians, pharmacists and psychologists.⁵¹⁻⁵⁴ Reliability was found to be 0.95 correlation with the FACIT-Fatigue scale.⁵³ Support for using PROMIS fatigue in heart failure patients was found in one study, although the reliability scores were not printed.⁵⁵

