The research associate will review all data collected for completeness and readability, correcting any errors prior to data analysis. We will collect "reason for drop out" if a participant stops the study. We will continue to try to schedule subsequent data collection interviews even if the participant is not able to complete a previous one. During each data collection session, team members will work with participants to encourage response to all items and will review data to ensure all data points are completed unless the participant prefers not to answer. Nonetheless, missing data will occur and this will be acknowledged in the analysis.⁷⁶ We will conduct initial analyses using the maximum likelihood approach, as it emphasizes the use of all available data. The use of random effects modeling techniques, in particular repeated measures mixed modeling, allows for missing data by adjusting the estimation process to account for bias resulting from data missing at random. Baseline data from those with and without missing data will be compared to determine whether there are systematic differences, using demographic and personal variables. If the data are not amenable to the maximum likelihood method random effects analysis, multiple imputation will be used as an alternative procedure for handling missing data. Multiple imputation produces results similar to maximum likelihood when used under identical conditions. We will use multiple imputation in the sensitivity analyses; this will allow for the comparison of study results under a variety of assumptions to assess the robustness of the findings.

Statistical Analysis

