Data analysis will be done using SPSS, v. 22; an alpha level of .05 will be used for all tests except where noted. Study measures will be examined using univariate statistics, including means, standard deviations and frequency distributions, and graphical techniques, such as box plots and histograms. Distributions for continuous outcome measures will also be examined for violations of normality using normal probability plots. If there is evidence of lack of normality for a particular outcome, transformations (e.g., logarithmic) will be used so that the distribution of the transformed variable more closely approximates normality. The analysis strategy to be used to test all aims is repeated measures analysis of variance (ANOVA). Each ANOVA model will include the main effects of Time (baseline, 6 weeks, 6 months' post intervention period) and Group (intervention and sham intervention), as well as the Time by Group

interaction. Post-hoc pairwise comparisons of means will be done using Fisher least significant difference procedure. The repeated measures models will be estimated using the MIXED procedure in SAS. This analysis will: **test the effect of NMES on muscle mass and strength in those with HF (Aim 1); evaluate the effect of NMES on exercise capacity and activity (Aim 2); and assess the effect of NMES on HF symptoms and quality of life (QOL); and finally, evaluate the effect of NMES on enrollment and utilization of a formalized exercise program (aim 4).** There will be a separate model for each outcome variable, and the significance of the main and interaction effects will indicate the effect of the intervention over time.

Power Considerations

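### Baseline is modelled as a free outcome in each arm and gender is left out, so the interaction has only change-score precision and the Group main effect is diluted by the pre-treatment visit

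*Combined protocol and SAP*

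**What the plan says.** Section 8 (Statistical Analysis) sets one model per outcome: "Each ANOVA model will include the main effects of Time (baseline, 6 weeks, 6 months' post intervention period) and Group", plus the Time by Group interaction. No covariate is named. The treatment effect is to be read from both kinds of term: "the significance of the main and interaction effects will indicate the effect of the intervention over time". Estimation is by mixed model: "The repeated measures models will be estimated using the MIXED procedure in SAS".

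Section 4 (Enrollment and Randomization) balances the arms on gender: "Randomization via minimization will be used in order to avoid an unbalanced number of women in the two comparison groups due to chance". Section 5 (Intervention and Sham/Wait List Control Conditions) has all baseline data collected before randomization.

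Section 5 (Instruments and Measures, item 7) collects demographics to "obtain potential confounding variables such as age, sex, race/ethnicity" and others. Section 8 gives these variables no role in the outcome models. Their only stated analytic use is under Missing Data: "Baseline data from those with and without missing data will be compared to determine whether there are systematic differences".

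**The concern.** Because baseline is measured before randomization, any difference between the arms at that visit is chance. The planned model nevertheless estimates a separate baseline mean for each arm. This has two consequences.

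- **Interaction.** It compares change from baseline between arms. That is valid, but it carries the full noise of the baseline measurement. Using the known equality of the baseline means, or baseline as a covariate, removes part of that noise.
- **Group main effect.** It averages over all three visits, one of which cannot show an effect. A constant post-treatment difference is multiplied by 2/3.

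The allocation factor is also missing. Where an outcome differs by gender, leaving out a factor on which the arms have been balanced makes the test of the Group main effect, or of a post-baseline group contrast, conservative.

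With 27 completers per arm, precision is scarce, and both baseline values and gender are already collected.

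**Working it through.** **Inputs from the documents.** 27 completers per arm (N = 54), three visits (m = 3), alpha 0.05, effect sizes f = 0.4 and 0.25 (Section 8, Power Considerations). The within-person correlation rho is described only as modest.

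**Assumptions.** Compound symmetry, complete data, variance 1 at each visit. The illustrative effect is 0.5 SD at both follow-ups; for two equal groups, f = 0.25 corresponds to a difference of 2 × 0.25 = 0.5 SD.

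**Step 1: reproduce the plan's power and find the rho it implies.** Noncentral F, with
- Group: lambda = f²Nm / (1 + (m − 1)rho), df 1 and 52
- Interaction: lambda = f²Nm / (1 − rho), df 2 and 104

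At rho = 0.33:
- Group, f = 0.4: lambda = 0.16 × 162 / 1.66 = 15.6, power 97.2% (stated 97%)
- Group, f = 0.25: lambda = 0.0625 × 162 / 1.66 = 6.10, power 67.9% (stated 69%)
- Interaction, f = 0.25: lambda = 0.0625 × 162 / 0.67 = 15.1, power 93.9% (stated 95%)

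All three are within 2 points for rho from 0.31 to 0.34. So 0.33 is implied by the plan but not stated in it.

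**Step 2: 6-week contrast, change score against baseline-adjusted.** The SE is sqrt((2/27)v), with v = 2(1 − rho) for change and v = 1 − rho² after adjustment. The ratio is (1 + rho)/2.

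| rho | v, change | v, adjusted | ratio | power for 0.5 SD, change to adjusted |
|---|---|---|---|---|
| 0.33 | 1.34 | 0.89 | 0.665 | 34% to 48% |
| 0.5 | 1.00 | 0.75 | 0.75 | 44% to 55% |
| 0.7 | 0.60 | 0.51 | 0.85 | 64% to 71% |
| 0.9 | 0.20 | 0.19 | 0.95 | 98.1% to 98.5% |

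At rho = 0.33, 27 per arm with adjustment is worth 27 / 0.665, or about 41 per arm without.

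**Step 3: mean of both follow-ups at rho = 0.33.** Change: v = (1 + rho)/2 + 1 − 2rho = 1.005. Adjusted: v = (1 + rho)/2 − rho² = 0.556. Power goes from 44% to 68%, provided the 0.5 SD effect persists to the later visit.

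**Step 4: Group main effect.** The effect is diluted to 0.5 × 2/3 = 0.33 SD, and the variance of a three-visit mean is (1 + 2rho)/3. Power is 37% at rho = 0.33, 31% at 0.5 and 27% at 0.7. It falls as the correlation rises, the opposite of Step 2.

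**Step 5: gender.** With gender balanced across arms and complete data, the variance of the Time by Group contrast is 0.1037 with and without a gender term (rho = 0.3), because a stable gender difference cancels within person. The Group main effect can gain: if gender explains an assumed 10% to 50% of the variance of participants' means, its SE is multiplied by sqrt(0.9) = 0.95 to sqrt(0.5) = 0.71, a fall of about 5% to 29%. The documents give no figure for that share.

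**The case against.** A reader might infer that the plan ignores baseline. It does not: baseline is a level of Time, and the interaction already compares change from baseline. The planned test is valid; the loss is one of efficiency.

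A reader might also infer that omitting gender widens every group comparison. Step 5 shows that this is not so for the interaction in balanced complete data. The gender point is confined to the Group main effect and post-baseline group contrasts.

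The gain depends on an unstated correlation. The reliability figures quoted in Section 5 are high: 0.92 for the dynamometer, 0.93 for the MLHFQ total, 0.76 to 0.99 for sit-to-stand, 0.978 to 0.99 for TUG. They are probably upper bounds for correlations over 6 weeks, but they show that 0.33 may be low for some outcomes. Against the planned two-degree-of-freedom interaction test, the adjusted 6-week contrast has 48% against 35% power at rho 0.33, 71% against 67% at 0.7, 85% for both at 0.8, and 98.5% against 99.1% at 0.9. For very stable measures, then, the 6-week contrast gains nothing over the planned test. This objection stands.

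It would be tempting to set the 35% of the planned interaction test against the 68% in Step 3. That mixes adjustment with a change of contrast; the unadjusted mean of both follow-ups already has 44%.

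Finally, the study calls itself exploratory, and Aim 4 enrollment has no baseline value. Both limit the reach of the point. Neither answers the dilution of the Group main effect, which worsens as correlation rises.

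**Conclusion.** The point holds as an avoidable loss of precision and a poorly chosen effect term, not as a bias or an invalid test. At the correlation implied by the plan's own power figures, the interaction gives up about a third of the single-visit variance. The loss is 25% at 0.5, 15% at 0.7 and only 5% at 0.9. The Group main effect understates a constant post-treatment effect by one third at any correlation and should not serve as evidence of treatment effect. Leaving out gender is a smaller matter: it can make the Group main effect conservative, by an amount the documents do not allow one to fix.

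These figures rest on compound symmetry, complete data, 27 per arm and, for power, an assumed 0.5 SD effect at both follow-ups. Actual correlations will differ by outcome.

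**What to change.** For each continuous outcome measured at baseline:

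- Constrain the baseline means to be equal across arms, or use the baseline value as a covariate for the two follow-up visits.
- Include gender as a fixed effect, with gender by time if wanted.
- Name the post-baseline group contrasts as the treatment effect, with 6 weeks first and the later visit also reported. Do not read the effect from the Group main effect averaged over all three visits.

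The baseline part does not apply to Aim 4 enrollment.

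The cost is about one or two degrees of freedom and a short change to the model specification in Section 8. No new data are needed.
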